4.1 General Concomitant Medication and Supportive Care Guidelines

No additional medication beyond VTE chemoprophylaxis (i.e. enoxaparin vs. apixaban) will be administered as part of the trial. VTE chemoprophylaxis is a normal part of clinical management following autologous breast reconstruction. The safety profile of apixaban will be studied in patients at highest risk for development of VTE, i.e. Caprini score ≥ 6 .

4.2 Criteria for Removal from Study

The experiment will terminate if the subject wishes to terminate study treatment or has adverse reaction to the medication that the treating physician deems withdrawal is necessary, or patient withdrawal of consent.

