The treatment period spans the duration of inpatient hospitalization. While hospitalized, patients will be evaluated daily for symptomatic VTE (DVT and/or PE) and bleeding events. After hospital discharge, patients will be encouraged to report all adverse events (AEs) including, but not limited to, signs/symptoms of DVT/PE and bleeding. Suspected DVT/PE will be evaluated with the appropriate diagnostic assessment, including but not limited to Duplex sonography, chest CT-angiography, or V/Q scan. A mandatory phone interview will take place on Day 90 (± 3 days) to confirm that no 90-day events had been diagnosed or were managed by another institution.

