6. DOSE MODIFICATIONS

We do not plan to adjust medication dose. In the absence of postoperative bleeding, the medication will be administered per protocol. The medication will be withheld and/or discontinued, however, in the setting of major bleeding or clinically relevant nonmajor bleeding (for definitions see 7.1.).

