7. ADVERSE EVENTS AND REPORTING PROCEDURES

7.1 Potential Adverse Events

The primary safety outcome is bleeding during the treatment period or until 2 days after the last dose of the study medication was administered (Lassen et al. NEJM 2020;26:2487-2498). Bleeding is categorized as major, clinically relevant nonmajor, or minor bleeding and as the composite of major and clinically relevant nonmajor bleeding. The definition of major bleeding is acute, clinically overt bleeding accompanied by one or more of the following findings: a decrease in the hemoglobin level of 2 g per deciliter or more over a 24-hour period; transfusion of 2 or more units of packed red cells; bleeding at a critical site (including intracranial, intraspinal, intraocular, pericardial, and retroperitoneal bleeding); bleeding into the operated joint, necessitating reoperation or intervention; intramuscular bleeding with the compartment syndrome; or fatal bleeding. Clinically relevant nonmajor bleeding includes acute, clinically overt episodes such as wound hematoma, bruising or ecchymosis, gastrointestinal bleeding, hemoptysis, hematuria, or epistaxis that does not meet the criteria for major bleeding. Bleeding is categorized as minor if it is clinically overt but is not adjudicated as major or clinically relevant nonmajor bleeding.

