11. STATISTICAL CONSIDERATIONS

11.1 Statistical Design

The primary study outcome is defined as overall bleeding event risk 90 days post-randomization. Secondary patient-oriented outcomes include risk of VTE events. Tertiary outcomes include: length of stay, location of patient on day 90 of follow up (home vs. SNF, etc), and clinically significant wound complications (infection, dehiscence, flap loss).

Process measures to be collected include time to starting anticoagulation after completion of skin closure, number of days patients received anticoagulation treatment, and timing of phone interview follow up.

Conservative estimates from recent retrospective study in over 1500 patients who underwent body contouring procedures (LMWH [N=454]; rivaroxaban [N=703], apixaban [N=415]) are used for our power analysis (37). Using standard formulas, with 80% power to detect a non-inferiority margin of -0.075, and assuming a 1.32% baseline in bleeding events among patients dosed on daily enoxaparin compared with a 1.73% rate of bleeding in direct oral anticoagulant (DOAC) arm patients over 90 days, our analysis expects enrollment size of 37 patients per arm. We conservatively estimate a 25% dropout rate over the course of the study, which results in a sample size of 100 (50 patients per arm).

The primary conclusions of this project will be analyzed based on intention-to-treat where all randomized patients will be analyzed within the groups they were originally allocated to. Two-sided 5% significance levels will be used to identify statistically significant results. Unadjusted analysis of the bleeding risk in apixaban use will be assessed using an exact Pearson chi-squared test. The outcome will be reported as an odds ratio with 95% confidence intervals. Baseline prognostic variables including age, BMI, Caprini score, Elixhauser comorbidity index score, procedure duration, unilateral vs. bilateral will be ascertained upon enrollment and reported by our study group. A subsequent covariate adjusted analysis will be undertaken with an adjusted logistic regression model.

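### Section 4.2 makes stopping the drug a ground for leaving the study, although the intention-to-treat analysis needs a 90-day outcome from every randomized patient

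*Combined protocol and SAP*

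**What the plan says.** The rule stands under the heading "4.2 Criteria for Removal from Study". It reads: "The experiment will terminate if the subject wishes to terminate study treatment or has adverse reaction to the medication", the second ground applying when the treating physician judges withdrawal necessary. Withdrawal of consent follows in the same sentence as a third ground. All three have the same stated consequence.

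Section 11.1, repeated in 9.1 and 11.4, sets what the analysis needs. The outcome: "The primary study outcome is defined as overall bleeding event risk 90 days post-randomization". The population: "all randomized patients will be analyzed within the groups they were originally allocated to". VTE is the secondary outcome. The same text allows for 25% dropout and gives no rule for a missing outcome.

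Three other places bear on follow-up:

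- Section 4: "A mandatory phone interview will take place on Day 90 (± 3 days". It neither includes nor exempts patients who have been removed.
- Section 6 has the drug held or stopped "in the setting of major bleeding or clinically relevant nonmajor bleeding". It says nothing about leaving the study.
- Section 7.1 gives the primary safety outcome a different window: "bleeding during the treatment period or until 2 days after the last dose of the study medication was administered".

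Study drug is given only during the inpatient stay (Section 4), and the trial is open-label (Section 2.4).

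**The concern.** An intention-to-treat analysis of a 90-day risk needs the 90-day outcome whether or not the patient stayed on the drug. If stopping the drug ends participation, a site that follows 4.2 to the letter has no duty to look for events after that point, and the promised analysis has gaps that the plan does not say how to fill.

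Two groups of outcomes are exposed. One is VTE up to day 90 in anyone who stops early, including those who stop because they bled. The other is bleeding up to day 90 in patients who stop for another reason, such as intolerance or preference, without having bled.

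Because treatment is open-label and one arm is oral and the other injected, the wish to stop and the physician's decision are both made knowing the arm. The rate of stopping, and the kind of patient who stops, may therefore differ between arms. Outcomes that were never collected cannot be recovered at the analysis stage.

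**Working it through.** **1. The passages side by side.**

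- *Trigger.* The heading of 4.2 refers to the study, not to treatment. Withdrawal of consent plainly ends participation, and the two treatment-related grounds share its sentence and its consequence. The literal reading is that all three end participation.
- *When it can apply.* Drug is given only in hospital, so the treatment-related grounds operate only during the stay. Stopping at discharge is planned and is not a trigger.
- *What is required.* Section 11.1 requires all randomized patients, with outcomes to day 90.
- *What bridges the two.* Nothing explicit. No section separates stopping the drug from leaving follow-up. SAE tracking in 7.2 runs to resolution or to 30 after the last dose, with no unit given.

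**2. The plan's sample size, reproduced.** Inputs from 11.1: bleeding risk 1.32% (enoxaparin) and 1.73% (DOAC), margin 0.075, power 80%, dropout 25%.

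n per arm = [p1(1−p1) + p2(1−p2)] × (z_α + z_β)² / (0.075 − 0.0041)²

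- Variance term: 0.01303 + 0.01700 = 0.03003.
- At one-sided 0.05: 0.03003 × (1.645 + 0.842)² / 0.0709² = 36.93, so 37 per arm.
- 37 / 0.75 = 49.3, so 50 per arm and 100 in total. This matches the plan.

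The match needs one-sided 0.05, whereas the plan states two-sided 5%. That is a separate matter, so both levels are shown below.

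**3. What retention is worth.** Power = Φ(0.0709 / √(0.03003/n) − z_α).

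| Followed per arm | One-sided 0.05 | One-sided 0.025 |
|---|---|---|
| 50 | 0.894 | 0.825 |
| 37 | 0.801 | 0.702 |

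These are normal approximations with very few expected events. The 37 row is the plan's general dropout allowance, not a forecast of removals under 4.2.

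**4. Scale for bleeding.** Expected bleeds per 50 patients are 50 × 0.0132 = 0.66 (enoxaparin) and 50 × 0.0173 = 0.87 (apixaban). The planned difference is +0.41 points. Losing every apixaban bleed would make it −1.32, a shift of 1.73. Losing every enoxaparin bleed would make it +1.73, a shift of 1.32.

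**5. Illustration with assumed inputs.** The documents give neither the share removed (f) nor the risk of those removed relative to those who stay (RR). If the events of removed patients go unobserved, the risk seen among those who stay is p / (f × RR + 1 − f).

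| f, RR | Loss in apixaban arm only: observed risk; difference | Loss in enoxaparin arm only: observed risk; difference |
|---|---|---|
| 10%, 3 | 1.73/1.2 = 1.44%; +0.12 | 1.32/1.2 = 1.10%; +0.63 |
| 25%, 10 | 1.73/3.25 = 0.53%; −0.79 | 1.32/3.25 = 0.41%; +1.32 |

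The sign of the shift depends entirely on which arm loses more. With RR = 1, the risk among those who stay is unbiased.

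**6. Scale for VTE.** The plan sets no VTE rate for the trial. Section 2.3 cites symptomatic VTE in up to 4% after abdominal-flap reconstruction. Taken as an upper assumption, this is 50 × 0.04 = 2 events per arm, so one uncollected VTE would be half of an arm's expected count.

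**The case against.** The best defence is that 4.2 means treatment only. The day-90 call is described as mandatory without exemption, the calendar in Section 8 schedules adverse event evaluation at discharge and at 90 days without requiring that the patient still be on drug, and days on anticoagulant are a planned process measure. This is a reasonable reading and may well be the intention. It does not settle the point, because the heading and the pairing with consent withdrawal point the other way, and no sentence tells a site which to follow.

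A second defence is that the window in 7.1 ends 2 days after the last dose, so little bleeding follow-up would be lost. That window conflicts with the 90 days in 11.1, and it does nothing for VTE.

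Several stronger readings are tempting and are not supported:

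- *That the rule loses the bleeds themselves, because Section 6 stops the drug for bleeding.* Section 6 removes nobody from the study, and a bleed that leads to stopping has already happened and counts as a primary event.
- *That lost bleeds favour a non-inferiority conclusion.* The direction depends on which arm loses more events, which the documents do not say. The stated analysis is an exact chi-squared test with an odds ratio, with no comparison against the margin.
- *That each lost patient is worth 2 percentage points (1/50).* This is so only if she had an unrecorded event.
- *That the 25% dropout reflects this rule.* The plan does not attribute it to any cause.

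**Conclusion.** The point holds as an inconsistency between a stated rule and the stated analysis. Taken literally, 4.2 lets patients who stop the drug in hospital leave before the 90-day outcome that 11.1 requires of everyone, and it sits uneasily with the mandatory call in Section 4. The exposure is mainly VTE after early stopping, then bleeding in patients who stop for reasons other than a bleed.

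The size and direction of any bias cannot be derived. At the plan's own rates, the expected effect of lost events on the bleeding difference is small against the 7.5-point margin (1.73 points if every apixaban bleed were lost). That limit rises if the true bleeding rate is above the planning rate. For VTE, with at most about 2 expected events per arm on the assumption above, a single missed event would matter to the description of the result.

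The conclusion rests on the literal reading of 4.2. If only treatment was meant, the change simply confirms it. It should be made because it is cheap and the data cannot be recovered afterwards.

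**What to change.** Reconcile 4.2 with Section 4 and Section 11.1 by splitting it in two:

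- **Stopping study drug, for any reason.** The patient stays in the study and has the discharge assessment and the day-90 call.
- **Withdrawal from the study.** Only when the patient withdraws consent to follow-up.

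Record the date and reason for each separately. The rules on when the drug is stopped are not touched. While editing, reconcile the 2-day window in 7.1 with the 90-day outcome in 11.1, so that it is clear how long bleeding is collected after stopping. A sentence in 11.1 on how a missing day-90 outcome is handled would cover those who do withdraw consent.

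Cost: a few sentences and a short CRF entry. The discharge assessment and the day-90 call are already scheduled, and the sample size stays at 100.

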4.3 Alternatives

The alternative is to not participate and receive the standard treatment of subcutaneous anticoagulant postoperatively.

5. INVESTIGATIONAL AGENT/DEVICE/PROCEDURE INFORMATION

5.1 Investigational Agent/Device/Procedure

We previously demonstrated that the majority of plastic surgery patients receive inadequate enoxaparin prophylaxis using fixed daily dosing (5). A follow-up study demonstrated a statistically significant reduction in postoperative VTE rate following twice daily administration of enoxaparin (6). The observed clinical differences are explained by differences in the rate of in-range peak anti-factor Xa levels (7).

Although enoxaparin is effective, disadvantages include the need for subcutaneous injection as well as dose adjustment based on anti-factor Xa levels. A potentially better alternative is the use of oral, direct factor Xa inhibitors. Importantly, this group has demonstrated superior outcomes in the orthopedic population when compared to enoxaparin (8, 9). Hence, it appears prudent to examine their role in the plastic surgery population.

This project will identify plastic surgery patients who meet criteria for postoperative VTE chemoprophylaxis and 1)

identify the rate of adverse drug events (ADE) following oral apixaban administration, 2) examine the rate of bleeding events in patients receiving oral apixaban versus subcutaneous enoxaparin, and 3) examine the rate of VTE in each group.

Review of enoxaparin mechanism and pharmacodynamics

Enoxaparin is a low molecular weight heparin commonly provided as chemical VTE prophylaxis in surgical patients. Enoxaparin accelerates the activity of antithrombin, which, in turn, accelerates the rate at which Factor Xa is inactivated. Factor Xa inactivation results in decreased conversion of prothrombin to thrombin. Inhibition of this critical step in the coagulation cascade decreases the likelihood that clot will form. Enoxaparin's peak response occurs at three to five hours after subcutaneous injection, with a half-life of seven hours. Enoxaparin metabolism occurs by metabolism in the liver and excretion via the kidneys. Patients with creatinine clearance of less than 30 mL/min demonstrate 30% decreased enoxaparin clearance. Enoxaparin exhibits linear pharmacokinetics and an inverse relationship between renal impairment and drug activity.

Review of apixaban mechanism and pharmacodynamics

Apixaban was introduced in 2014 and is a highly selective inhibitor of free and prothrombinase-bound FXa. It has a half-life of 8 to 15 hours and multiple pathways of elimination, including renal and fecal excretion with minimal drug-drug interactions. The recommended dose for VTE prophylaxis is 2.5mg PO BID. The superiority of apixaban over enoxaparin has been demonstrated in landmark trials of hip and knee replacement, where lower rates of VTE were seen without increased bleeding.

For clinicaltrials.gov and Stanford Clinical Trials Directory compliance

Intervention Description

Patients will be assigned to the respective study groups postoperatively upon arrival in the PACU. Hence, surgeons are blinded at the time of surgery as to study group assignment. Chemoprophylaxis will continue for the duration of the hospitalization. Planned timing of prophylaxis initiation with apixaban and enoxaparin is in alignment with published data from the multicenter VTEPS study, respectively (3, 8, 9, 38). Prophylaxis duration is compliant with guidelines from the American Society of Plastic Surgeons (11). All patients will receive mechanical prophylaxis in the form of sequential compression devices prior to the induction of general anesthesia and continued for the duration of inpatient stay.

The treatment period spans the duration of inpatient hospitalization. While hospitalized, patients will be evaluated daily for symptomatic VTE (DVT and/or PE) and bleeding events. After hospital discharge, patients will be encouraged to report all adverse events (AEs) including, but not limited to, signs/symptoms of DVT/PE and bleeding. Suspected DVT/PE will be evaluated with the appropriate diagnostic assessment, including but not limited to Duplex sonography, chest CT-angiography, or V/Q scan. A mandatory phone interview will take place on Day 90 (± 3 days) to confirm that no 90-day events had been diagnosed or were managed by another institution.

Arms/Groups:

Group A: Apixaban 2.5 mg PO BID starting 12-16 hours after completing skin closure.

Group B: Enoxaparin 40 mg SC QD starting 12-16 hours after completing skin closure.

5.2 Availability

Stanford Hospital & Clinics has both agents readily available.

5.3 Agent Ordering

The agent will be requested through the EPIC physician ordering system.

5.4 Agent Accountability

The agent will be kept secure as standard process for the pharmacy so as to avoid access to unauthorized persons.

6. DOSE MODIFICATIONS

We do not plan to adjust medication dose. In the absence of postoperative bleeding, the medication will be administered per protocol. The medication will be withheld and/or discontinued, however, in the setting of major bleeding or clinically relevant nonmajor bleeding (for definitions see 7.1.).

7. ADVERSE EVENTS AND REPORTING PROCEDURES

7.1 Potential Adverse Events

The primary safety outcome is bleeding during the treatment period or until 2 days after the last dose of the study medication was administered (Lassen et al. NEJM 2020;26:2487-2498). Bleeding is categorized as major, clinically relevant nonmajor, or minor bleeding and as the composite of major and clinically relevant nonmajor bleeding. The definition of major bleeding is acute, clinically overt bleeding accompanied by one or more of the following findings: a decrease in the hemoglobin level of 2 g per deciliter or more over a 24-hour period; transfusion of 2 or more units of packed red cells; bleeding at a critical site (including intracranial, intraspinal, intraocular, pericardial, and retroperitoneal bleeding); bleeding into the operated joint, necessitating reoperation or intervention; intramuscular bleeding with the compartment syndrome; or fatal bleeding. Clinically relevant nonmajor bleeding includes acute, clinically overt episodes such as wound hematoma, bruising or ecchymosis, gastrointestinal bleeding, hemoptysis, hematuria, or epistaxis that does not meet the criteria for major bleeding. Bleeding is categorized as minor if it is clinically overt but is not adjudicated as major or clinically relevant nonmajor bleeding.

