1. OBJECTIVES

1.1. Primary Objective

To examine the rate of bleeding events in patients receiving oral apixaban versus subcutaneous enoxaparin.

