2.4 Study Design

For clinicaltrials.gov and Stanford Clinical Trials Directory compliance

- **Prevention:** protocol designed to assess one or more interventions aimed at preventing the development of a specific disease or health condition
- **Parallel:** one of two groups in parallel for duration of study.
 - 2 intervention arms.
 - **Open:** no masking is used
 - Study is randomized.
 - Safety/Efficacy; Pharmacokinetics.

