7.2 Adverse Event Reporting

All bleeding/thrombotic Adverse Events will be tracked by the research team using an adverse event log. All unanticipated adverse events and SAE's will be reported to the IRB. Annual summaries of adverse events will be reported to the IRB.

Adverse events will be graded according to CTCAE v4.03. Both Serious and Non-Serious Adverse Events will be clearly noted in source documentation and listed on study specific Case Report Forms (CRFs). The Protocol Director (PD) or designee will assess each Adverse Event (AE) to determine whether it is unexpected according to the Informed Consent, Protocol Document, or Investigator's Brochure, and related to the investigation. All Serious Adverse Events (SAEs) will be tracked until resolution, or until 30 after the last dose of the study treatment.

SAEs CTCAE Grade 3 and above, and all subsequent follow-up reports will be reported to the Stanford Cancer Institute Data and Safety Monitoring Committee (DSMC) using the study specific CRF regardless of the event's relatedness to the investigation. Following review by the DSMC, events meeting the IRB definition of 'Unanticipated Problem' will be reported to the IRB using eProtocol within 10 working days of DSMC review, or within 5 working days for deaths or life-threatening experiences.

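### Section 7.1 keeps a joint-surgery criterion for major bleeding that no participant can meet, and counts bruising as clinically relevant with no rule for the injection site, although only enoxaparin is injected

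*Combined protocol and SAP*

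**What the plan says.** Bleeding is the main question of the trial. The primary objective (section 1.1) reads "To examine the rate of bleeding events in patients receiving oral apixaban versus subcutaneous enoxaparin", and section 11.1 states: "The primary study outcome is defined as overall bleeding event risk 90 days post-randomization". Sections 9, 9.1 and 11.4 repeat this outcome. None of them says which kinds of bleeding count or refers to a definition.

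The only bleeding definition is in section 7.1. Major bleeding is acute, overt bleeding with at least one listed finding: a hemoglobin fall, transfusion, a critical site, "bleeding into the operated joint, necessitating reoperation or intervention", intramuscular bleeding with compartment syndrome, or death. The next category is set out thus: "Clinically relevant nonmajor bleeding includes acute, clinically overt episodes such as wound hematoma, bruising or ecchymosis", followed by several other kinds of bleed. The last category is a remainder: "Bleeding is categorized as minor if it is clinically overt but is not adjudicated as major or clinically relevant nonmajor bleeding". Section 7.1 ends its window 2 days after the last dose.

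Three other statements matter. Section 2.4 says that "no masking is used". Section 4 gives apixaban by mouth and enoxaparin by subcutaneous injection. Section 6 relies on the 7.1 categories: "The medication will be withheld and/or discontinued, however, in the setting of major bleeding or clinically relevant nonmajor bleeding".

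**The concern.** The definition looks carried over from joint surgery. The page range cited in 7.1 (2487-2498) matches reference 8, a hip-replacement trial, although the year and volume differ. Two things follow.

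(a) The operated-joint criterion is empty here. A hematoma of the breast, flap or abdominal donor site that goes back to the operating room does not become major on that ground. It can fall into the same category as a bruise, and a table of bleeding by severity could then understate major bleeding.

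(b) A bruise at a needle site can arise in only one arm. If unmasked staff count such bruises, the enoxaparin rate rises because of the route of administration and not because of systemic bleeding. The comparison then moves in favor of apixaban. With so few bleeds expected, a handful of bruises could dominate the result.

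**Working it through.** **Part (a): the text side by side.** Section 3.1 admits only women having breast reconstruction with a free abdominal flap, so the joint criterion can never be met. A reoperated surgical-site bleed can still be major through the hemoglobin, transfusion, critical-site, compartment-syndrome or fatal criterion. If none applies, it is a wound hematoma or another overt bleed below major.

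- Overall bleeding count: unchanged, because the event is counted under either label.
- Composite of major and clinically relevant nonmajor bleeding: unchanged, because both labels are inside it.
- Section 6 trigger: unchanged, because both labels activate it.
- Recording: unchanged. Section 7.2 says "All bleeding/thrombotic Adverse Events will be tracked by the research team using an adverse event log", and events are CTCAE-graded.

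Only the split between major and nonmajor is affected. Sections 9 and 11 do not name a major-bleeding rate as an outcome.

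**Part (b): inputs.** From section 11.1: enoxaparin bleeding rate 1.32%, DOAC rate 1.73%, margin 7.5 points (written -0.075), power 80%, 37 per arm before 25% dropout, 50 per arm randomized, two-sided 5% level, exact Pearson chi-squared test, result reported as an odds ratio. The documents give no injection-bruise rate.

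*The plan's own figure.* With unpooled variance and a one-sided 5% level:

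n = (1.645 + 0.842)² × (0.0132 × 0.9868 + 0.0173 × 0.9827) / (0.075 - 0.0041)² = 36.9, so 37 per arm.

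37 / 0.75 = 49.3, so 50 per arm and 100 in total. The plan's numbers reproduce on that basis.

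*Expected events.* Enoxaparin: 50 × 0.0132 = 0.66. Apixaban: 50 × 0.0173 = 0.87.

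*Effect of one bruise.* One otherwise event-free enoxaparin patient counted for an injection-site bruise adds 1/50 = 2.0 points to the enoxaparin rate.

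*Effect on the planned analysis.* Start from one bleed per arm (apixaban 1/50, enoxaparin 1/50), and add bruises to enoxaparin only. The odds ratio is apixaban over enoxaparin, and p is the two-sided conditional exact value.

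| Bruises added | Apixaban v enoxaparin | Odds ratio | p |
|---|---|---|---|
| 0 | 1/50 v 1/50 | 1.00 | 1.00 |
| 3 | 1/50 v 4/50 | (1/49)/(4/46) = 0.23 | 0.36 |
| 6 | 1/50 v 7/50 | (1/49)/(7/43) = 0.13 | 0.059 |
| 7 | 1/50 v 8/50 | (1/49)/(8/42) = 0.11 | 0.031 |

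The estimate moves early. The test passes 5% only at the seventh bruise. The starting point of 1 v 1 is an illustration, chosen because the plan expects about one event or fewer in each arm.

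**The case against.** The strongest reply to (b) is that it needs two steps the text does not supply. The first is that 7.1 governs the 90-day outcome. Sections 9 and 11 do not cite 7.1, and 7.1 attaches its categories to a primary safety outcome with a shorter window. Section 9 even says that no safety issue is being measured. The second is that staff would record a needle-site bruise as an acute, clinically overt episode. The plan's own rate hints otherwise: 454 × 0.0132 = 6.0 bleeds among the LMWH patients of the cited retrospective study, which is few if injection bruises had been counted. This is only a hint, since that study's definition is not in the documents. All of this stands as a limit on the point. It does not remove it: without 7.1 the primary outcome has no definition at all, and in-hospital bruises fall inside both windows.

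A second reply is that a sponsor may legitimately count route-related bleeding. The objective compares an oral with a subcutaneous drug, and section 5.1 names the injection as a disadvantage of enoxaparin. This also stands. The documents require a stated rule, not exclusion of these bruises.

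A reader might infer more than the text supports in two places. One is that three or four bruises would carry the trial across its 7.5-point margin. The margin appears only in the sample-size calculation, whereas the stated analysis is a two-sided exact test with an odds ratio. The other is that the joint wording biases the primary outcome. It does not, because a reoperated bleed is counted under either label.

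**Conclusion.** The point holds in two parts of unequal weight.

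Part (a) is a criterion that is wrong for this operation as written. Its effect is confined to the major versus nonmajor label of reoperated surgical-site bleeds.

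Part (b) is a gap in the text that could reach the primary comparison, on condition that the 7.1 categories define the 90-day outcome and that injection-site bruises are recorded as bleeding. Under those conditions the shift is 2.0 points per affected patient at 50 per arm, always in favor of apixaban. Its total size cannot be estimated from the documents. Statistical significance is fairly resistant (seven bruises from 1 v 1), but the reported odds ratio is not (three bruises).

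Moving bruises to the minor category would not settle the matter, because the plan does not say whether overall bleeding includes minor bleeding. Both parts are worth correcting before events are classified by unmasked staff. Section 7.1 speaks of adjudication but describes no adjudicator, blinded review or rules.

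**What to change.** 1. In the outcome definition in section 7.1, replace operated joint with operated site (breast, flap or abdominal donor site).
2. In sections 9 and 11, state which 7.1 categories make up overall bleeding, and whether minor bleeding is among them.
3. Record bruising confined to the injection site as a separate case report form item and tabulate it by arm. Prespecify the bleeding comparison both with and without it. The sponsor should state in advance which of the two is primary.
4. Section 6 relies on the 7.1 categories, so check the two sections for consistency after the rewording. No withholding rule is proposed here.

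The cost is some wording, one case report form field and one extra analysis. The definition also becomes slightly less comparable with that of the hip-replacement trial. No safety information is lost, since injection-site bruises are still reported.
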